5.2 Data Source

Truven MarketScan Claims Database (01JUL2013-30JUN2018)

MarketScan offers the largest proprietary claims-based convenience sample available, with 69 million unique patients since 1996. In the most recent data year, the databases contain data on 29 million covered lives. The stability of MarketScan data sources allows superior continuity of patients over multiple years, which is generally longer than other claims databases. This is due to the fact that the majority of the data is sourced from large employers. Employer-provided data also allow tracking of patients across health plans. This tracking ability is useful because people change health plans more often than they change jobs, and these data are able to capture patients who are “lost” in plan-based data sources—upward of 17% of patients in those databases. In the most recent 5 years of MarketScan data, nearly 29 million patients (73%) have at least 12 months of continuous enrollment.

The MarketScan claims databases contain complete information on outpatient prescriptions. These databases afford distinct advantages over others that track only prescription fills, as the data allow for disease type identification (from medical claims) and can be used to determine whether clinical, demographic, and provider characteristics influence prescribing patterns. Because individual patients’ prescription fills are recorded, therapies prescribed concurrently (and presumably used in combination) can also be identified. This provides vital information about actual drug use patterns, as opposed to individual drug prescription trends.

[2019-8636] Observational Study Protocol

VHA Database (01APR2013-31MAR2018)

The VHA is the largest integrated health care system in the US, providing quality care at efficient prices for >9 million veterans across the country. According to VA estimates, there were about 22 million living US veterans in 2014.²³

The size and structure of the VHA system differs from most private care organizations. The system includes:

- 153 medical centers;
- 136 nursing homes;
- 207 Vet Centers;
- 882 ambulatory care and community-based outpatient clinics;
- 45 residential rehabilitation treatment programs;
- 92 comprehensive home-based care programs;
- 13,000 physicians;
- nearly 55,000 nurses; and
- >9 million enrollees^{24,25}

[2019-8636] Observational Study Protocol

Figure 4 VHA Data Elements

VHA Database					
Medical SAS® Data		Decision Support System Data		Corporate Data Warehouse	Vital Status Data
Inpatient dataset	Outpatient dataset	Clinical NDE	Core NDE		

 • Acute Care: Inpatient (IP) stays for acute care at a medical center lasting ≥24 hours. • Extended Care: IP stays in VA community centers and care in VA nursing homes. 
Datasets within acute and extended care
 
 • Main: Hospital IP stay. Example variables include: 
 ○ 1º/2º diagnosis ○ Length of stay • Bed: IP stay under a specified physician service. Example variables include: 
 ○ 1º/2º diagnosis ○ Admission and discharge date ○ Length of stay • Procedure: Procedure in IP stay. Example variables include: 
 ○ Procedure date ○ ICD-9/10-CM codes • Surgery: Surgery in IP stay. Example variables include: 
 ○ Surgery date ○ ICD-9/10-CM codes 	
 • Event: One ambulatory/outpatient encounter by a patient. Example variables include: 
 ○ Encounter date ○ Procedure codes ○ Diagnosis codes 	
 • Laboratory results: Results for a specific list of laboratory tests, inpatient and outpatient. Example variables include: 
 ○ Service date ○ Result value ○ Test unit • Pharmacy: Prescription utilization and costs, inpatient and outpatient. Example variables include: 
 ○ Dispensing date ○ Quantity ○ Days supply ○ Cost 	
 • Discharge: Costs for inpatient services at discharge. Example variables include: 
 ○ Admission and discharge date ○ Length of stay ○ Total cost • Outpatient: Costs for outpatient services. Example variables include: 
 ○ Primary diagnosis ○ Visit date ○ Total cost 	
 • National repository of VHA administrative and clinical data. • Vital signs information such as blood pressure, height, weight, etc. • Example variables include: 
 ○ Vital type ○ Result ○ Date taken and entered 	
 • Provides mortality information. • One record per person who has received care or benefits, or enrolled in the VHA. • Provides enrolment information for each patient. • Example variables include: 
 ○ Death date ○ Race ○ Sex

IP: inpatient stays; NDE: National Data Extracts; VA: Veterans Administration; 1º/2º: primary/secondary.

The VHA Medical SAS® datasets are national administrative data for VHA-provided health care used by veterans. The datasets are provided in SAS format by fiscal year (01OCT–30SEP). These data are extracted from the National Patient Care Database and maintained by the VHA Office of Information at the Austin Information Technology Center (the central repository for VA data).

VHA Medical SAS Inpatient Datasets

The Medical SAS Inpatient datasets cover the care received in acute, extended care settings. Within these categories, there are 4 datasets:

- main—a patient's inpatient stay (episode of care);
- bed section—a patient's inpatient stay under a specified physician treating for a specialty service;
- procedure—1 day's procedure during an inpatient stay; and
- surgery—1 day's surgery during an inpatient stay.

Inpatient variables describing each hospital admission include date, time, facility, and the primary diagnosis at admission. Discharge data include date, time, destination (e.g., home, hospice,

[2019-8636] Observational Study Protocol

community nursing home), type of discharge (e.g., regular, transfer to another hospital, death), and length of stay (LOS).

VHA Medical SAS Outpatient Datasets

Each outpatient data record represents 1 date of service for 1 outpatient and includes the facility identifier, date, and time of visit. Visits on a single day to multiple clinics, laboratories, and treatment programs are reported.

Outpatient care is reported by diagnoses (ICD-9-CM and ICD-10-CM codes) and procedures (CPT codes), including dates and times.

Currently, there is 1 Medical SAS dataset for outpatient care:

- Event: 1 ambulatory encounter (coded as Decision Support System [DSS] Identifier).

VHA Decision Support System

The VHA DSS is a managerial cost accounting system based on the commercial software Eclipsys[®]. The VHA must populate data elements required to allocate VHA costs to VHA products (goods and services provided during patient care). Towards that end, the VHA has modified Eclipsys to interact with VistA and other VA national databases. The VHA DSS was introduced in 1994 and fully implemented in all facilities by 1999.

The VHA DSS data files comprise a longitudinal, secondary relational database combining selected clinical and cost data. The DSS provides a mechanism for integrating expenses, workload, and patient utilization. DSS information supports process and performance improvements by measuring quality of care, clinical outcomes, and financial impact. Within a fiscal year, periodic rollups of production data are performed to produce year-to-date, non-destructive examinations.

DSS Clinical National Data Extract

- Laboratory Results: laboratory test results for a specific list of tests (inpatient and outpatient)
- Pharmacy: pharmacy prescription utilization and costs (inpatient and outpatient)

VA Vital Status Files

The VHA Vital Status File (VSF) contains the date of death for veterans and eligible non-veterans who have received care from the VHA since 1992, have enrolled in the VHA, or have received compensation or pension benefits from the VHA since 2002. The VHA VSF file is updated quarterly.

Sources for vital status available to the VA include the VA Beneficiary Identification and Record Locator System, the Death Master File from the Social Security Administration (SSA), patient treatment file, and Medicare vital status. The primary source for dates of death in the Vital Status file is the SSA Death Master File. The impetus for the development of the VHA VSF was the VA Information Resource Center's (VIREC) Veterans Administration National Death Index (NDI) Data Merge Project. This work was supported by funding from the Health Services Research and

[2019-8636] Observational Study Protocol

Development Service (SDR 03-157) and VIREC (SDR 98-004). The project compared the dates of death from sources available within the VA to those obtained from the NDI, a repository of data from death certificates that is considered the gold standard for mortality data in the United States. The study found that using a combination of the available death data sources in the VA resulted in death ascertainment nearly as complete as using the NDI.

The stability of VHA data sources allows for superior analysis of the continuity of care of patients over multiple years.

Data Limitations

While claims data are extremely valuable for the efficient and effective examination of health care outcomes, they are collected for administration and not research. Therefore, the use of claims data has certain limitations. For example, the presence of a claim for a filled prescription does not indicate that the medication was consumed or taken as prescribed. Medications filled over-the-counter or provided as samples by the physician cannot be observed in the claims data. The presence of a diagnosis code on a medical claim does not necessarily indicate a positive presence of disease, as the diagnosis code may be incorrect or included as rule-out criteria rather than actual disease. And certain information that is not readily available in claims could influence study outcomes, such as clinical and disease-specific parameters.

5.3. Study Population

5.3.1 Selection Criteria

U-500R Syringe Initiators [Index Event a]

Inclusion Criteria

Patient will be included if they:

- had ≥ 1 prescription claim for U-500R vial during the identification period (VHA: 01JAN2014–30JUN2017; Truven: 01JUL2014–30JUN2017), with the first prescription claim for U-500R vial designated as index Event a (U-500R syringe initiation), and the date designated as the index date;
- had ≥ 2 claims with an ICD-9/10-CM code (Appendix 1) for T2DM in any position (primary/secondary) at any time prior to the index date;
- were aged ≥ 18 years on the index date;
- had continuous health plan enrollment with medical and pharmacy benefits for ≥ 9 months pre- and post-index event;
- had ≥ 1 prescription claim for any insulin other than U-500R in the pre-index period;
- had ≥ 1 HbA1c measurement within 90 days pre-index or 30 days post-index event;
- had ≥ 1 HbA1c measurement after the 30-day post-index period at any time in the 9-month post-index period;

[2019-8636] Observational Study Protocol

- had claims indicating TDD >180 in the post-index period;
- had claims indicating TDD >180 in the pre-index period; and

Exclusion Criteria

Patient will be excluded if they:

- had both T1DM and T2DM, had no oral anti-diabetic drug (OADs; Appendix 1) other than metformin, and the ratio between the number of T1DM and T2DM claims >0.5 at any time in the study period (VHA: 01APR2013–31MAR2018; Truven: 01JUL2013–30JUN2018);
- had previous use of U-500R in the 9-month pre-index period;
- had ≥ 1 claim with an ICD-9/10-CM code (Appendix 1) for secondary diabetes, gestational diabetes, diabetes complicating pregnancy, childbirth, puerperium, or non-clinical diabetes at any time during the 9-month pre-index period;
- had claims indicating pump use (Appendix 2) in the 9-month post-index (follow-up) period;
- had claims indicating TDD above 2000 units/day at any time in the pre-index or post-index periods; or
- had claims indicating insulin use other than U-500R in the post-index period.

U-500R Kwikpen Initiators [Index Event **b**]Inclusion Criteria

Patient will be included if they:

- had ≥ 1 prescription claim for U-500R Kwikpen administration during the identification period (VHA: 01JAN2014–30JUN2017; Truven: 01JUL2014–30JUN2017), with the first prescription claim for U-500R Kwikpen administration designated as Index Event **b**, and the date designated as the index date;
- had ≥ 2 claim with an ICD-9/10-CM code (Appendix 1) for T2DM in any position (primary/secondary) at any time prior to the index date;
- were aged ≥ 18 years on the index date;
- had continuous health plan enrollment with medical and pharmacy benefits for ≥ 9 months pre- and post-index event;
- had ≥ 1 prescription claim for any insulin other than U-500R (Table 1) in the pre-index period;
- had ≥ 1 HbA1c measurement within 90 days pre-index or 30 days post-index event;
- had ≥ 1 HbA1c measurement after the 30-day post-index period at any time in the follow-up period;
- had claims indicating TDD >180 in the post-index period;

[2019-8636] Observational Study Protocol

- had claims indicating TDD >180 in the pre-index period; and

Exclusion Criteria

Patient will be excluded if they:

- had both T1DM and T2DM, had no OADs (Appendix 1) other than metformin, with the ratio between the number of T1DM and T2DM claims >0.5 at any time in the study period (VHA: 01APR2013–31MAR2018; Truven: 01JUL2013–30JUN2018);
- had previous use of U-500R in the 9-month pre-index period;
- had ≥ 1 claim with a ICD-9/10-CM code (Appendix 1) for secondary diabetes, gestational diabetes, diabetes complicating pregnancy, childbirth, puerperium, or non-clinical diabetes at any time during the pre-index period;
- had evidence of pump use (Appendix 2) in the post-index period;
- had claims indicating TDD above 2000 units/day at any time in the pre-index or post-index periods; or
- had claims indicating insulin use other than U-500R in the post-index period.

Sample selection criteria for any U-500R Initiators [Index Event c]Inclusion Criteria

Patient will be included if they:

- had ≥ 1 prescription claim for U-500R syringe or Kwikpen administration during the identification period (VHA: 01JAN2014–30JUN2017; Truven: 01JUL2014–30JUN2017), with the first prescription claim for U-500R syringe or Kwikpen administration designated as Index Event c, and the date designated as the index date;
- had ≥ 2 claim with an ICD-9/10-CM code (Appendix 1) for T2DM in any position (primary/secondary) at any time prior to the index date;
- were aged ≥ 18 years on the index date;
- had continuous health plan enrollment with medical and pharmacy benefits for ≥ 9 months pre- and post-index event;
- had ≥ 1 prescription claim for any insulin other than U-500R (Table 1) in the pre-index period ;
- had ≥ 1 HbA1c measurement within 90 days pre-index or 30 days post-index event;
- had ≥ 1 HbA1c measurement after the 30-day post-index period at any time in the follow-up period;
- had claims indicating TDD >180 in the post-index period; and
- had claims indicating TDD >180 in the pre-index period

[2019-8636] Observational Study ProtocolExclusion Criteria

Patient will be excluded if they:

- had both T1DM and T2DM, had no OADs (Appendix 1) other than metformin, with the ratio between the number of T1DM and T2DM claims >0.5 at any time in the study period (VHA: 01APR2013–31MAR2018; Truven: 01JUL2013–30JUN2018);
- had previous use of U-500R in the 9-month pre-index period;
- had ≥ 1 claim with a ICD-9/10-CM code (Appendix 1) for secondary diabetes, gestational diabetes, diabetes complicating pregnancy, childbirth, or puerperium, or non-clinical diabetes at any time during the pre-index period;
- had evidence of pump use (Appendix 2) in the follow-up period;
- had claims indicating TDD above 2000 units/day at any time in the pre-index or post-index periods; or
- had claims indicating insulin use other than U-500R in the post-index period.

Note:

- All high-dose U-500R patients will be defined by having an average TDD of >180 units per day, with no additional insulin used concomitantly or no U-500R pump use.
- Since the Truven claims database does not include lab data, the ≥ 1 HbA1c criterion will be removed from the selection criteria while using this database.
- For analysis conducted using the Truven claims database, the pre-index period and the post-index period will be 12 months instead of 9 months.
- The corresponding ICD-9/10 codes for all the diagnoses and the NDC codes for the insulin treatments are provided in Appendix 1.

Subgroup analysis:

- Elderly (≥ 65 years) patients among each of the high-dose U-500R Kwikpen, high-dose U-500R syringe, and any high-dose U-500R initiator cohorts will be flagged, and a subgroup analysis will be performed comparing the treatment patterns and outcomes (HbA1c and hypoglycemia) before and after U-500R initiation.
- Patients with a TDD of 201-300 units in the post-index period among each of the high-dose U-500R Kwikpen, high-dose U-500R syringe, and any high-dose U-500R initiator cohorts will be flagged, and a subgroup analysis will be performed comparing the treatment patterns and outcomes (HbA1c and hypoglycemia) before and after U-500R initiation.
- (Optional): Patients with a TDD of >300 units in the post-index period among each of the high-dose U-500R Kwikpen, high-dose U-500R syringe, and any high-dose U-500R initiator cohorts, and a subgroup analysis will be performed comparing the treatment patterns and outcomes (HbA1c and hypoglycemia) before and after U-500R initiation.

Table 1. Classification of Insulin Products

Insulin Class	Generic Name	Product Name
Inhaled Insulin	Insulin Human Inhaled	AFREZZA
		EXUBERA
		EXUBERA COMBINATION PACK 12
		EXUBERA COMBINATION PACK 15
		EXUBERA KIT
Intermediate-acting Insulin	Insulin Human Zinc (lente)	HUMULIN L
	Insulin Human Isophane (nph)	HUMULIN N (NPH)
		HUMULIN N (NPH) KWIKPEN
		HUMULIN N PEN
		INSULATARD HUMAN INSULIN
		MIXTARD HUMAN INSULIN 70/30
		NOVOLIN N
		NOVOLIN N (NPH)
		NOVOLIN N INNOLET
		NOVOLIN N PENFILL
		RELION HUMULIN N
		RELION NOVOLIN N INNOLET
Long-acting Insulin	Insulin Glargine Soln Pen-Injector	Basaglar KwikPen
	Insulin Glargine, Recombinant	LANTUS
		LANTUS SOLOSTAR
	Insulin Detemir	LEVEMIR
		LEVEMIR FLEXPEN
		LEVEMIR FLEXTOUCH
	Insulin Glargine, Recombinant	TOUJEO
Insulin Degludec	TRESIBA	
Pre-mixed Insulin	Insulin Lispro Protamine/Insulin Lispro	HUMALOG MIX 50/50
		HUMALOG MIX 75/25
		HUMALOG MIX 75/25 PEN
	Insulin Human Isophane (nph)/Insulin Human Regular	HUMULIN
		HUMULIN 50/50
		HUMULIN 70/30
		HUMULIN 70/30 KWIKPEN
		HUMULIN 70/30 PEN

[2019-8636] Observational Study Protocol

Insulin Class	Generic Name	Product Name
	Insulin Beef Regular/Insulin Pork Isophane (nph)	ILETIN NPH I
	Insulin Human Isophane (nph)/Insulin Human Regular	NOVOLIN 70/30
		NOVOLIN 70/30 INNOLET
		NOVOLIN 70/30 PENFILL
	Insulin Aspart Protamine/Insulin Aspart	NOVOLOG MIX 70/30
		NOVOLOG MIX 70/30 FLEXPEN
	Insulin Human Isophane (nph)/Insulin Human Regular	RELION HUMULIN 70/30
		RELION NOVOLIN 70/30
		RELION NOVOLIN 70/30 INNOLET
	Rapid-acting Insulin	Insulin Glulisine
APIDRA SOLOSTAR		
Insulin Lispro, Recombinant		HUMALOG
		HUMALOG KWIKPEN
		HUMALOG PEN
		LISPRO-PFC
Insulin Aspart, Recombinant		NOVOLOG
		NOVOLOG FLEXPEN
		NOVOLOG PENFILL
Short-acting Insulin		Insulin Human Regular, Buffered
	Insulin Human Regular	HUMULIN R
		INSULIN HUMAN REGULAR
		NOVOLIN 70/30 PENFILL
		NOVOLIN N PENFILL
		NOVOLIN R
		NOVOLIN R INNOLET
		NOVOLIN R PENFILL
		RELION HUMULIN R
	RELION NOVOLIN R	
Insulin Human Regular, Buffered	VELOSULIN BR	
U-500R	Insulin Human Regular	HUMULIN R CONCENTRATED U-500
		HUMULIN R CONCENTRATED U-500 KWIKPEN
	INSULIN REGULAR (HUMAN)	HUMULIN R U-500 KWIKPEN

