The treatment patterns and outcomes of two sub-groups are of great interests. The first subgroup is the elderly. Given the highly concentrated nature of U-500R, physicians have hesitation in using U-500R with their elderly patients. Even though elderly accounted for about 50% of the U-500R initiators in an ongoing study (full RWE cohort), no studies have explicitly examined the safety and efficacy of U-500R in elderly. Information on the effectiveness and safety of U-500R among elderly will be valuable to HCPs and patients. The other subgroup of interests are those whose U-500R daily dose is in the range of 201-300 units/day. While most physicians are confident with the use of U-500R when patients insulin needs exceed 300 units/day, this is not the case in the range of 201-300 units for some physicians. Currently only less than 20% of patients on 201-300 units/day insulins use U-500R (internal data-on-file). Therefore, it is important to understand the compliance, effectiveness, and safety among those who were on 201-300 units/day of U-500R insulin. Additionally, the U-500R Kwikpen was launched in 2016. Therefore, a 9-months pre- and post-index period will be applied in the VHA to ensure adequate sample size due to the recent launch of the Kwikpen. Since VHA does not have reliable cost data, Truven database is used to understand out-of-pocket costs and will be assessed using a 12-months pre- and post-index period to ensure deductibles are properly captured for all patients.

The aim of this study is to provide a comprehensive understanding of U-500R in high-dose cohort (defined by having an average TDD of >180 units per day, with no additional insulin used concomitantly with U-500R or pump use), including compliance, effectiveness, safety, and out-of-pocket costs, rather than just one particular aspect of U-500R. Ideally, an integrated database with both claims and EMR data will be needed for such a study. Unfortunately, while VHA database is an integrated claims and EMR database, it lacks reliable costs data. As a result, out-of-pocket costs aspect will be examined separately using IBM MarketScan data.

[2019-8636] Observational Study Protocol**4. Objectives****4.1 Research Objectives****Research Objective 1: Treatment Patterns**

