5.3.2 Subject Groups

After applying the selection criteria, our analysis will focus on the following cohorts.

Index Event a

[2019-8636] Observational Study Protocol

- high-dose U-500R Syringe Initiators Cohort: Patients who initiated U-500R syringe administration (Index Event **a**) on their index date.

Index Event b

- High-dose U-500R Kwikpen Initiators Cohort: Patients who initiated U-500R Kwikpen administration (Index Event **b**) on their index date.

Index Event c

- Any high-dose U-500R Initiators Cohort: Patients who initiated U-500R (vial or Kwikpen; Index Event **c**) on their index date. The first prescription claim for vial or Kwikpen will be defined as the index date.

Note: In each of the abovementioned cohorts, subgroups of elderly patients (≥ 65 years), patients with TDD 201-300 units/day and (optional) those who had TDD >300 units/day will be identified for the subgroup analysis.

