Out-of-pocket costs	Truven: Inpatient service table, outpatient service table, outpatient pharmacy claims table	
Out-of-pocket pharmacy costs will be computed among T2DM patients before and after high-dose U-500R syringe initiation, high-dose U-500R Kwikpen initiation, and any high-dose U-500R initiation.
 
Out-of-pocket pharmacy costs will be further classified into:
 
 • Diabetes-related out-of-pocket pharmacy costs (i.e., the costs associated with any insulins and AHAs [sulfonylureas, TZD, biguanides, meglitinides, alpha-glucosidase inhibitors, DPP-4 inhibitors, SGLT-2, bile acid sequestrant, fixed-dose combination, GLP-1, pramlintide) • Insulin-related out-of-pocket pharmacy costs • All-cause out-of-pocket pharmacy costs (i.e., all the pharmacy costs in the 12 months period) 
Costs will be adjusted to 2018 US dollars using the annual medical care and drug costs components of the Consumer Price Index (CPI) to reflect inflation.

Note: Treatment pattern in the Truven database will be conducted using the 12-month pre- and post-index period.

[2019-8636] Observational Study Protocol

6. Sample Size and Statistical Methods**6.1 Determination of Sample Size**

The preliminary sample sizes for the VHA databases from 2013–2018 are shown below. This study will use the most recent 5 years of data available.

Table 3. Preliminary Sample Size

Database	Counts
VHA (01APRIL2013–31MARCH2018)	
Kwikpen:	
Evidence of U-500R Kwikpen during the identification period	2,596
Evidence of T2DM	2,536
≥1 HbA1c in the pre-index and post-index periods	741
After applying other inclusion/exclusion criteria and excluding patients with pump use along with U-500R Kwikpen	647
Syringe Use:	
Evidence of U-500R syringe use during the identification period	5,162
Evidence of T2DM	4,956
≥1 HbA1c in the pre-index and post-index periods	1,930
After applying other inclusion/exclusion criteria and excluding patients with pump use along with U-500R syringe	1,766

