6.4 Other Analyses**6.4.1 Outcomes Analyses**

All the analyses will be performed separately in VHA and Truven claims database.

Research Objective 1: Primary Objective 1Descriptive Analysis

All study variables including demographics, clinical characteristics, and treatment patterns of insulin (i.e., TDD, adherence, prescription fill rate, claim gaps, and concomitant medication use)

[2019-8636] Observational Study Protocol

will be analyzed descriptively before and after high-dose U-500R Kwikpen initiation, high-dose U-500R syringe initiation, and any high-dose U-500R initiation.

Numbers and percentages will be provided for dichotomous and polychotomous variables. Means and standard deviations (SDs) will be provided for continuous variables. To determine the statistical significance of before and after values, McNemar's test will be used for categorical variables, and the paired t-test will be used for continuous variables.

Multivariate Analysis

A mixed linear model will be used to evaluate factors associated with insulin adherence in the pre- and post-index periods among high-dose U-500R Kwikpen initiators, high-dose U-500R syringe initiators, and any high-dose U-500R initiators. Mixed linear models are used for studies with a longitudinal feature in which a continuous outcome variable is measured for the same subject repeatedly over the time period. Based on the distribution of the data, observations measured for the same subject are likely to be correlated over the study period, and these measurements are considered *multilevel* data. In addition, mixed linear models have a mixed effect consisting of both fixed and random effects. Time-varying and time-invariant variables can both be included in the model. In the current model, adherence (measured at 2 time intervals [before and after the index event: U-500R initiation]) will be considered the dependent variable. Observed TDD will be designated as the time varying covariate in the model (measured both before and after the index event), and the time-independent covariates will include the demographic and clinical characteristics.

The complete list of time varying and time-independent covariates will include:

- age;
- sex;
- race;
- BMI;
- Pre-index CCI score;
- observed TDD from claims; and
- time (pre/post).

Note:

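### In VHA the paired HbA1c entry rule also restricts the treatment-pattern analyses and the descriptive hypoglycemia comparison, neither of which uses HbA1c

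*Protocol*

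**What the plan says.** Protocol Section 5.3.1 lists two HbA1c conditions among the inclusion criteria for each of the three index events. The baseline condition is that the patient "had ≥ 1 HbA1c measurement within 90 days pre-index or 30 days post-index event". The follow-up condition, as worded for syringe initiators, is that the patient "had ≥ 1 HbA1c measurement after the 30-day post-index period at any time in the 9-month post-index period"; the Kwikpen and any-U-500R lists have an equivalent line.

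Section 5.3.2 builds one set of cohorts from these lists: "After applying the selection criteria, our analysis will focus on the following cohorts". It defines age and dose subgroups but no analysis set specific to an objective.

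The rule is lifted for Truven, which holds no laboratory data: "the ≥ 1 HbA1c criterion will be removed from the selection criteria while using this database". Section 6.4.1 adds that "All the analyses will be performed separately in VHA and Truven claims database", and the note under Table 2 that "Treatment pattern in the Truven database will be conducted using the 12-month pre- and post-index period". Costs (Exploratory Objective 3) come from Truven alone; Section 3 says that the "out-of-pocket costs aspect will be examined separately using IBM MarketScan data".

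Table 3 in Section 6.1 gives preliminary VHA counts, with one row labelled "≥1 HbA1c in the pre-index and post-index periods".

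**The concern.** The outcomes of Primary Objective 1 are observed dose, proportion of days covered (PDC), fills, claim gaps and concomitant medication. All come from pharmacy records. The adherence model in Section 6.4.1 adjusts for age, sex, race, BMI, comorbidity score, dose and period, not for HbA1c. The descriptive hypoglycemia comparison (McNemar and paired t-test) does not use HbA1c either. In VHA, a patient without paired HbA1c is nevertheless removed from both.

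Two things are at stake.

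- **Precision.** The HbA1c step is by far the largest loss in Table 3. Section 3 justifies the 9-month window by the need for enough patients after the recent Kwikpen launch. What remains is then divided into an elderly subgroup and dose subgroups.
- **Selection on a post-index event.** A value after day 30 requires laboratory contact during follow-up, the same period in which PDC and claim gaps are measured. Section 3 recognizes this kind of problem for another rule: it gives up studying persistence because the monotherapy exclusion removes some early discontinuers. It makes no similar remark about the HbA1c rule.

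**Working it through.** **Inputs** (Section 6.1, Table 3, VHA)

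| Row | Kwikpen | Syringe |
|---|---|---|
| Type 2 diabetes | 2,536 | 4,956 |
| HbA1c in both periods | 741 | 1,930 |
| Other criteria and pump exclusion | 647 | 1,766 |

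The table has no row for the any-U-500R cohort. The document gives counts only; the percentages below are derived.

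**1. Loss at the HbA1c step** = 1 − n after / n before

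- Kwikpen: 2,536 − 741 = 1,795; 1,795/2,536 = 70.8%
- Syringe: 4,956 − 1,930 = 3,026; 3,026/4,956 = 61.1%

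**2. Share of all exclusions after the diabetes row**

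- Kwikpen: 1,795/(2,536 − 647) = 1,795/1,889 = 95.0%
- Syringe: 3,026/(4,956 − 1,766) = 3,026/3,190 = 94.9%

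**3. Do these counts describe the high-dose cohort?** The last step removes only 94/741 = 12.7% (Kwikpen) and 164/1,930 = 8.5% (syringe). Section 3 says that a cut at 180 units would exclude more than 25% of observed patients. If that held here, at most 0.75 × 741 = 556 Kwikpen and 0.75 × 1,930 = 1,447.5 syringe patients could remain, both below the printed 647 and 1,766. With the Kwikpen median of 176 units given in the same section, no more than about half of 741 (about 370) would pass. Table 3 therefore appears to precede the requirement of a total daily dose (TDD) above 180 units.

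**4. Illustration of the upper end.** Assume that patients without paired HbA1c would pass the later criteria at the same rate as those with it:

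- Kwikpen: 2,536 × 647/741 = 2,214, against 647
- Syringe: 4,956 × 1,766/1,930 = 4,535, against 1,766
- Ratio of confidence interval widths: √(741/2,536) = 0.54; √(1,930/4,956) = 0.62

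Before the TDD rule, the gain thus lies between nothing (647 and 1,766) and these figures. The assumption cannot be checked from the document.

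**5. Where HbA1c is used in VHA** (Section 6.4.1)

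| Analysis | HbA1c used? |
|---|---|
| Objective 1, descriptive | No |
| Objective 1, adherence model | No |
| Objective 2, HbA1c | Yes, outcome |
| Objective 2a, descriptive | No |
| Objective 2a, zero-inflated model | Yes, covariate before and after index |

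**6. What the rule guarantees.** The baseline window runs to 30 days after index, so both required values may be post-index. The rule ensures laboratory contact after initiation but not before it. Table 2 counts a glucose of 70 mg/dL or less from the laboratory file as a hypoglycemia event, so event ascertainment may depend on this contact.

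**The case against.** A single VHA cohort serves a stated aim. Section 3 wants dose and adherence read together with HbA1c and hypoglycemia, and values VHA because it integrates claims and clinical records. Using the same patients throughout is a defensible choice. It does not require discarding the other patients: the common cohort can be kept for Objective 2 and as a sensitivity analysis for Objective 1.

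Precision may also be adequate already. At n = 647 the 95% half-width of a paired mean change is 1.96/√647 = 0.08 SD, and at an assumed 300 after the TDD rule it is 0.11 SD. That stands for the whole cohort, so no shortfall is demonstrated. It does not answer the selection question.

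Four stronger readings are tempting, and the documents do not support them.

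- *The rule binds every objective.* It does not. It is removed for Truven, which covers all of Objective 3 and a second run of the treatment patterns. That removal does not show the rule to be inessential, because the stated reason is the absence of laboratory data.
- *Hypoglycemia does not need HbA1c at all.* The multivariable model lists HbA1c before and after index as a time-varying covariate, so patients without paired values would drop out of it as specified. Adding patients without laboratory follow-up could also worsen under-detection of low glucose.
- *The high-dose cohort loses 61% to 71%.* Table 3 is preliminary and sequential. Enrollment, washout and prior insulin use have no rows of their own, so patients lost at the HbA1c step might have failed later criteria anyway.
- *The retained patients are more adherent, so PDC is biased upward.* No data in the document show this. The comparisons are within patient, and a bias in the change is not demonstrated.

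**Conclusion.** The point holds for VHA Primary Objective 1 and for the descriptive hypoglycemia comparison. Both are limited to patients with paired HbA1c by a rule that neither analysis uses. In the preliminary counts the step removes 70.8% (Kwikpen) and 61.1% (syringe) of patients with type 2 diabetes, about 95% of all later exclusions in each column. This takes the Table 3 row to reflect the HbA1c criteria only. The corresponding share of the high-dose cohort cannot be derived, and the figures of 2,214, 4,535, 54% and 62% are illustrations under equal later retention.

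Requiring a value after day 30 conditions adherence outcomes on later contact with care. That is a reason to examine the selection, not evidence of bias in a known direction. Since the protocol itself fixes the rule as general eligibility, this is not a detail left open for an analysis plan.

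**What to change.** - Move both HbA1c criteria from general VHA eligibility (Section 5.3.1) to an analysis set for Primary Objective 2 and the multivariable hypoglycemia model.
- Run VHA Primary Objective 1, including the adherence model and its subgroups, in all patients who meet the other criteria. Repeat it in the paired-HbA1c cohort as a sensitivity analysis.
- Report the descriptive hypoglycemia comparison in both sets, and note that laboratory glucose ascertainment may differ between them.
- Tabulate baseline characteristics of patients with and without paired HbA1c.
- Extend Table 3 to show the count after the TDD rule, with and without the HbA1c criteria.

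The cost is protocol wording, one more analysis set on data already held, and sample sizes that differ by objective and need a clear footnote.
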